## 2) Best Confirmed Overall Response (Measurable Disease at Baseline) by Location of Metastatic Disease

Output ID: t\_rs\_best\_byloc\*

Repeat t\_rs\_best\* output by Location of Metastatic Disease as on the “Disease History of advanced or metastatic BCC” CRF page.

## 3) Best Confirmed Overall Response (Non-Measurable Disease at Baseline)

Output ID: t\_rs\_nonm\*

Repeat t\_rs\_best\* output for patients with non-measurable disease at baseline.

Programming Note:

- Percentages are calculated based on the number of patients with a non-measurable disease at baseline and histologically confirmed BCC.
- Only patients with non-measurable disease at baseline and histologically confirmed BCC should be included in the table.

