- Tumor assessment (the majority of the patients in this study have locally advanced BCC and, in this disease setting, measurable tumors are accessible to evaluation by physical examination). Objective responses using RECIST, v1.1 should be confirmed by repeat assessments at least 4 weeks after initial documentation of response:
 - Measurable tumors accessible to evaluation by physical examination should be assessed every 4 to 8 weeks throughout the study from the time of the first dose, regardless of dosing delays

- If assessment requires imaging, baseline CT and/or MRI should be performed within a maximum of 28 days prior to the first dose of study drug and, if such scans demonstrate evidence of disease, follow-up imaging studies (CT and/or MRI) should be performed every 8 to 16 weeks from the time of the first dose, regardless of dosing delays, or per institutional standards. The same imaging technique (CT or MRI) should be used for each patient throughout the study
- In metastatic BCC patients (newly enrolled after approval of the Study Protocol, version 4.0), imaging at baseline (CT and/or MRI scan) should be performed within a maximum of 28 days before the first dose. Follow-up imaging studies (CT and/or MRI scan) should be performed every 8 weeks (± 5 days) from the time of the first dose, regardless of dosing delays. The same imaging technique (CT or MRI) should be used for each patient throughout the study
- Other imaging techniques may be performed as clinically indicated, but should not be used for determining tumor response
- Patients with non-measurable disease at baseline should be assessed for disease progression when clinically indicated and in accordance with standard clinical practice. For metastatic patients, assessment of non-measurable disease should be according to RECIST version 1.1.
- In selected sites, patients will complete the Skindex-16 Quality of Life questionnaire after Cycle 1 and after Cycle 6 (i.e., after 6 months of treatment) for the patients still on study (see Main Protocol Section 5.5. and Appendix 5)
- Patients with metastatic BCC (newly enrolled after approval of the Study Protocol, version 4.0) will complete the M.D. Anderson Symptom Inventory (see Main Protocol Section 5.6 and Appendix 6) at every visit, prior to having any other assessments performed

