2.4 EVALUATION OF RESPONSE

2.4.1 Time Point Response (Overall response)

It is assumed that at each protocol specified time point, a response assessment occurs. [Table 1](#) provides a summary of the overall response status calculation at each time point for patients who have measurable disease at baseline.

When patients have non-measurable (therefore non-target) disease only, [Table 2](#) is to be used.

Table 1 Time Point Response – Target (w/wo Non-Target) Lesions

Target lesions	Non-target lesions	New lesions	Overall response
CR	CR	No	CR
CR	Non-CR/non-PD	No	PR
CR	Not evaluated	No	PR
PR	Non-PD or not all evaluated	No	PR
SD	Non-PD or not all evaluated	No	SD
Not all evaluated	Non-PD	No	NE
PD	Any	Yes or No	PD
Any	PD	Yes or No	PD
Any	Any	Yes	PD

CR = complete response, PR = partial response, SD = stable disease, PD = progressive disease, and NE = inevaluable.

Appendix 1 New Response Evaluation Criteria in Solid Tumors, Version 1.1: Modified Excerpt from Original Publication with Supplementary Explanations (1) (cont.)

Table 2 Time Point Response – Non-Target Lesions Only

Non-target lesions	New lesions	Overall response
CR	No	CR
Non-CR/non-PD	No	Non-CR/non-PD ^a
Not all evaluated	No	NE
Unequivocal PD	Yes or No	PD
Any	Yes	PD

CR = complete response, PD = progressive disease, and NE = inevaluable.
^a a 'Non-CR/non-PD' is preferred over 'stable disease' for non-target disease since SD is increasingly used as endpoint for assessment of efficacy in some trials so to assign this category when no lesions can be measured is not advised.

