## Output Specifications: Efficacy Tables

Best Response:

1) Best Confirmed overall response.

RSPT01	
Output ID: t_rs_best_*
 

● Analysis Population: Patients with measurable disease at baseline, excluding patients without histologically confirmed BCC. Outputs will be repeated for different population combinations - please see the LoPO for details of these combinations, and the Efficacy Population section for details on populations.

● Column Variables: Disease Status (Locally Advanced, Metastatic)

● Column Totals: Totals of non-missing Disease Status

● Analysis Variables: Response variable is the Best Overall Response: Complete Response, Partial Response, Stable Disease, Progressive Disease, Not evaluable, or Missing.

● Statistics and Calculation Methods: Use proq freq.

○ Display Patients with histologically-confirmed measurable disease at baseline

○ CIs for Best Overall Response Rate presented in the table are displayed as percentages, i.e. the actual values multiplied by 100.

○ <math>\alpha</math> level for CIs is 2-sided 5%.

○ Method of Clopper-Pearson is to be used to derive 95% CI for proportion.

● Numeric Precision and Formatting of Statistics: Use standard display in the mockup

● Optional Subsetting: Display Response categories i.e. Complete Response, Partial Response, Stable Disease, Progressive Disease, Missing, or Not evaluable, are displayed with percentage.

---------------	--

Programming Notes:

- Best Overall Response (BOR) would be Complete Response (CR) if subject had CR on each of two tumor assessments which are greater than or equal to 23 days apart (with either no other tumor assessments in between or the tumor response between these two assessments is CR or Not Evaluable (NE)).

- Best Overall Response would be Partial Response (PR) if subject's best overall response is not CR and the subject had two tumor assessments greater than or equal to 23 days apart with the response of the first assessment being PR and the second being PR or CR (with either no other tumor assessments in between or the tumor response between these two assessments being CR, PR, or NE).

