- Best Overall Response would be Stable Disease (SD) if subject's best overall response is not CR or PR, and there is at least one response assessment of CR, PR or SD with minimum of 51 days after First Dose Date without any Progressive Disease (PD) in between.
- Best Overall Response would be Progression Disease (PD) if subject's best overall response is not CR, PR, or SD, and if there is at least one response assessment of PD.
- Best Overall Response would be Not Evaluable (NE) if subject's best overall response is not CR, PR, SD, or PD, and there is at least one response assessment of NE.
- BOR would be PD if PD occurred before satisfying any of the above criteria of Best Overall Response.
- Patients who achieve best overall response of CR or PR are considered a responder.
- Best overall response rate is defined as the number of patients with a CR or PR observed at two consecutive assessments  $\geq 4$  weeks apart ( $\geq 23$  days) divided by the total number of patients with histologically confirmed measurable disease at baseline.
- N in column headings is the number of patients with a measurable or non-measurable disease at baseline and histologically confirmed BCC. Percentages are calculated based on the number of patients with a measurable disease at baseline and histologically confirmed BCC.
- Display only Responder and 95%CI for Best Overall Response Rate.

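### The SAP's best-response table for non-measurable disease reuses the measurable-disease categories, which have no place for Non-CR/non-PD, the Appendix 1 result for disease control

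*SAP*

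**What the plan says.** **SAP, Best Response, item 3 (t_rs_nonm\*).** The instruction is to repeat t_rs_best\* "output for patients with non-measurable disease at baseline". Two programming notes follow. One sets the denominator: "Percentages are calculated based on the number of patients with a non-measurable disease at baseline and histologically confirmed BCC". The other limits the table to those patients. Neither changes a response category or a derivation rule.

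**SAP, Best Response, item 1 (t_rs_best\*), which item 3 inherits.** "Response variable is the Best Overall Response: Complete Response, Partial Response, Stable Disease, Progressive Disease, Not evaluable, or Missing". CR and PR need confirmation at least 23 days later. SD applies when neither is met and "there is at least one response assessment of CR, PR or SD with minimum of 51 days after First Dose Date", with no PD in between. PD applies "if subject's best overall response is not CR, PR, or SD, and if there is at least one response assessment of PD". NE comes next. A patient with CR or PR counts as a responder.

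**Protocol, section 5.3.6 and Appendix 1, section 2.4.1.** Section 5.3.6 makes RECIST v1.1, as given in Appendix 1, the response standard. Appendix 1 directs that Table 2 be used when a patient has non-measurable disease only. Its outcomes are CR, Non-CR/non-PD, NE and PD. The footnote prefers Non-CR/non-PD to SD and warns that "to assign this category when no lesions can be measured is not advised".

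**Protocol synopsis, Treatment Phase Assessments (also sections 5.3.2 and 5.3.6).** "Patients with non-measurable disease at baseline should be assessed for disease progression when clinically indicated", following ordinary practice. RECIST v1.1 is named explicitly for the metastatic patients in this group.

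**The concern.** The table uses a vocabulary that the protocol's own response criteria do not give to these patients. Non-CR/non-PD is what Table 2 assigns to a patient whose non-target disease persists without progressing, and the SAP rules have no slot for it. PR is kept as a category and counts toward the responder rate, although Appendix 1, section 2.3.1, defines PR by the summed diameters of target lesions. The SAP, under Measurable/Non-Measurable Disease, defines this group by the absence of a target lesion at baseline.

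What is at stake is how disease control is described in this group. A patient held without progression for two years could look unassessed, or look like a primary progressor. If PR was entered, a response rate could be quoted for patients in whom partial response is undefined.

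**Working it through.** The plan gives no figure for this output, so there is nothing to reproduce. The check applies the SAP rules, in their stated order, to visit records written in Table 2 categories.

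**Inputs**
- Order of rules (SAP, Best Response, item 1): confirmed CR (two assessments at least 23 days apart), confirmed PR (same gap), SD (a CR, PR or SD at 51 days or later, before any PD), PD, NE.
- Missing is what remains. The SAP lists it as a category but gives no rule for it.
- Visit categories: Appendix 1, Table 2.
- Spacing: eight-weekly visits (day 56, 112, and so on) are my illustration. For records made up only of Non-CR/non-PD, NE or PD, the SAP result does not depend on spacing, because Non-CR/non-PD never enters a rule.

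**Results**

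| Visit record | SAP rules as written | With a Non-CR/non-PD category (see fix) |
|---|---|---|
| Non-CR/non-PD at 13 visits, to day 13 × 56 = 728; no PD | Missing | Non-CR/non-PD |
| Non-CR/non-PD at 12 visits, to day 12 × 56 = 672; PD on day 728 | PD | Non-CR/non-PD |
| PD at first visit, day 56 | PD | PD |
| 13 visits, one NE, the rest Non-CR/non-PD; no PD | NE | Non-CR/non-PD |
| Non-CR/non-PD day 56; CR days 112 and 168 (56 days apart, at least 23) | CR | CR |
| Non-CR/non-PD day 56; single CR day 112; Non-CR/non-PD day 168 | SD | Non-CR/non-PD |
| SD entered at every visit to day 728, or at 12 visits and then PD | SD | Non-CR/non-PD, counted in a footnote |

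**Reading the table**
- Rows 1, 2 and 4: the same clinical course, long control, lands in three different categories, none of which describes it.
- Rows 2 and 3: control to day 672 cannot be told apart from progression at day 56.
- Row 6: SD is reported although no visit recorded it.
- Row 7: if sites entered SD, the SAP rules run without difficulty, but the output is the category that the Table 2 footnote advises against.
- Rows 3 and 5: early PD and confirmed CR are classified correctly either way. A patient whose visits are all NE is also correctly NE.

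**What the SAP already recognises.** The Overall Lesion Assessment and Non-Target Lesion Assessment listings show NON CR/PD as a non-target response. No best-response rule uses it or maps it to SD.

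**Reach.** The main response rate (protocol section 8.2.1.1; SAP item 1) is restricted to measurable disease. PFS uses the dates of first treatment, PD, death or last assessment, not the best-response category. The same best-response derivation sets the asterisk in the Overall Lesion Assessment listing, which covers the intent-to-treat patients apart from those without histological confirmation. The flag is therefore affected for non-measurable patients.

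**The case against.** **The result depends on coding that cannot be seen.** The visit-level overall response comes from a CRF page whose code list is not in the documents. In the mock Overall Lesion Assessment listing, NON CR/PD appears only in the non-target column, and the overall response column shows SD, PR, CR and PD. This stands: Missing, NE or PD follows only if visits were recorded per Table 2. The mock does not settle the matter, because every example row has a target-lesion response. The other branch, SD or PR entered, departs from Appendix 1 in a different way.

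**RECIST may not be routine for most of these patients.** The protocol names it explicitly only for metastatic non-measurable disease, and the SAP's Summary of Deaths mock-up shows 1119 of 1215 patients as locally advanced. How many of them had non-measurable disease is not stated. This leaves some doubt about how often Table 2 was used, but section 5.3.6 opens with a general commitment to Appendix 1, and the SAP chose to produce a response table for this group.

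**The disputed categories may not be shown.** The item 1 template displays every category with percentages, while its last programming note limits display to responders and the interval. A responder-only table would hide the misclassification, though not a PR count or the listing flag. The conflict is unresolved in the SAP.

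**Appendix 1 gives no best-response rule for this category.** Its Table 3, for confirmed responses, has no Non-CR/non-PD row. That is true, so any derivation has to be written into the SAP and labelled as the SAP's own.

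**Tempting stronger readings.** A reader might infer that every non-measurable patient without a confirmed CR is misreported. The rules do not support that: first-visit PD and all-NE records are classified correctly. A reader might also infer that durable control was in fact reported as Missing or PD. The documents cannot show this without the code list.

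**Conclusion.** The mismatch is explicit in the text. The SAP derives best response for non-measurable disease with categories and rules that do not correspond to Appendix 1, Table 2, and none of its rules accepts Non-CR/non-PD. If visits were recorded per Table 2, durable control is reported as Missing, NE or PD. If SD or PR was entered, the table carries values that Appendix 1 discourages or cannot define without target lesions. Either way a stated rule is needed.

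The reach is narrow: t_rs_nonm\* and the best-response flag in one listing. The main response rate, the count of confirmed CRs and PFS do not change. The responder count in this table would change only if PRs had been recorded. The number of patients affected cannot be computed, because the documents do not give the number with non-measurable disease. This is worth correcting, but it does not bear on the trial's main safety or efficacy results.

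**What to change.** For t_rs_nonm\*, replace the inherited categories with confirmed CR, Non-CR/non-PD, PD, NE and Missing, and add these rules:

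- Assign Non-CR/non-PD when best response is not a confirmed CR and at least one qualifying assessment falls at or beyond the SAP's existing 51-day minimum and before any PD.
- Qualifying assessments are Non-CR/non-PD and an unconfirmed CR. Leaving out the unconfirmed CR would send a patient with a single CR on day 112, and no Non-CR/non-PD visit from day 51 on, to Missing, or to PD if progression followed.
- Count any recorded SD or PR as Non-CR/non-PD, with a footnote giving the number so treated. Leave the investigator-recorded values unchanged in the listings.
- Then apply PD, NE and Missing in that order, and define Missing.
- Give the Clopper-Pearson interval for confirmed CR only.
- State that all categories are displayed for this output, which settles the conflict between the item 1 template and its last programming note.
- Use the same derivation for the flag in the Overall Lesion Assessment listing for these patients.

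The cost is a few lines of SAP text and programming on data already collected. The table will no longer share its categories with t_rs_best\*, so the two cannot be read row by row. The 51-day minimum is carried over for consistency. Because these patients are assessed as clinically needed, someone seen only before day 51 still cannot qualify. Patients whose target-lesion field is blank remain outside both tables, as the SAP already provides.

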## Duration of Response:

TTET01	
Output ID: t_tte_OBJRDR_*
 

● Analysis Population: Intent-to-Treat Patients with measurable disease at baseline, excluding patients without histologically confirmed BCC. Outputs will be repeated for different population combinations - please see the LoPO for details of these combinations, and the Efficacy Population section for details on populations.

● Column Variables: Disease Status (Locally Advanced, Metastatic)

● Column Totals: Totals of non-missing Disease Status

● Analysis Variables: Duration of response in Months

● Statistics and Calculation Methods: Use proc freq and proc lifetest.

○ <math>\alpha</math> level for CIs is 2-sided 5%.

○ Use proc lifetest to obtain time to event (Median, Percentiles) information. The 95% confidence interval for the median is calculated using the Brookmeyer & Crowley method.

○ Range, 25th and 75th Percentiles are displayed.

● Numeric Precision and Formatting of Statistics: Use standard display in the mockup

---------------	--

### Programming Note:

- Duration of response will be calculated only for patients whose confirmed best response is CR or PR.
- Duration of response is the interval between the Date of First Response and the Date of Progressive Disease or Death, and is calculated only for patients with confirmed best response of CR or PR at two consecutive assessments  $\geq 23$  days.
- Patients without Progression of Disease or Death will be censored at the date of last tumour assessment and the duration of response is calculated using the interval between Date of First Response and the date of last tumour assessment.
- N would be the number of patients with a measurable or non-measurable disease at baseline and histologically confirmed BCC.
- Percentages are based on the number of patients with a measurable disease at baseline and histologically confirmed BCC, and who had a CR or PR.
- Duration of response will be calculated in Months.

## Time to Response:

TTET01	
Output ID: t_tte_TMTRS_*
 

● Analysis Population: Intent-to-Treat Patients with measurable disease at baseline, excluding patients without histologically confirmed BCC. Outputs will be repeated for different population combinations - please see the LoPO for details of these combinations, and the Efficacy Population section for details on populations.

● Column Variables: Disease Status (Locally Advanced, Metastatic)

● Column Totals: Totals of non-missing Disease Status

● Analysis Variables: Time to response in patients with Best Overall Response (BOR) and patients without BOR in Months

● Statistics and Calculation Methods: Use proc freq and proc lifetest.

○ <math>\alpha</math> level for CIs is 2-sided 5%.

○ Use proc lifetest to obtain time to event (Median, Percentiles) information. The 95% confidence interval for the median is calculated using the Brookmeyer & Crowley method.

○ Range, 25th and 75th Percentiles are displayed.

● Numeric Precision and Formatting of Statistics: Use standard display in the mockup

---------------	---

### Programming Note:

- Time to response is defined as the interval between the date of first treatment and the date of first documentation of confirmed CR or PR (whichever occurs first).
- Patients without CR or PR will be censored at the date of last tumour assessment.
- N would be the number of patients with a measurable or non-measurable disease at baseline and histologically confirmed BCC.
- Percentages are based on the number of patients with a measurable disease at baseline and histologically confirmed BCC.

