The best ORRs (confirmed complete and confirmed partial responders) together with the corresponding 95% Pearson-Clopper confidence intervals will be presented. A listing of tumor assessments and best overall response will also be presented.

Estimates for the survivor function for the time-to-event endpoints, including PFS, OS, time to response, and duration of response, will be displayed graphically using Kaplan-Meier (KM) curves. Estimates for the median time to event and the corresponding two-sided 95% confidence interval will be presented with the estimates for the other quartiles and the associated ranges (minimum, maximum). The estimates and KM curves will be presented for the ITT population.

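### Time to response by Kaplan-Meier censors patients who progress or die without responding, so it overstates the probability of response and its median cannot be read as the time by which half of patients responded

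*SAP*

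**What the plan says.** The SAP's Time to Response table is built on "Intent-to-Treat Patients with measurable disease at baseline, excluding patients without histologically confirmed BCC". Its analysis variable is "Time to response in patients with Best Overall Response (BOR) and patients without BOR in Months", so the risk set is not limited to responders. The clock runs from first treatment to "the date of first documentation of confirmed CR or PR". For estimation the instruction is "Use proc lifetest to obtain time to event (Median, Percentiles) information", with a 95% interval for the median and the 25th and 75th percentiles. The Programming Note gives the censoring rule: "Patients without CR or PR will be censored at the date of last tumour assessment".

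Protocol section 8.2.1.1 calls for the same family of methods: "Estimates for the survivor function for the time-to-event endpoints, including PFS, OS, time to response, and duration of response, will be displayed graphically using Kaplan-Meier". It defines time to response but gives it no censoring rule.

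Three neighbouring provisions matter:

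- The SAP's Best Response notes assign a best response of PD when progression comes before any response category has been met.
- Duration of response is restricted to confirmed responders.
- PFS counts progression and death as events.

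Neither document specifies a competing-risk estimate, or a summary of time to response among responders only.

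**The concern.** Kaplan-Meier treats a censored patient as someone who could still have the event later, at the same rate as those still under observation. That is reasonable for a patient still on treatment at the data cut. It is not reasonable for a patient who has died, or who has progressed before responding. Removing these patients from the risk set as censored shares their probability out among those who remain, so one minus Kaplan-Meier rises above the proportion who actually respond.

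At stake is the reading of a published descriptive result. A median time to response invites the reader to think that half of the patients had responded by then. If it stands beside a response rate near or below one half, the two tables can appear to disagree.

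**Working it through.** The plan gives no figure for time to response, so there is none to reproduce. The check asks how far the Kaplan-Meier median can depart from its natural reading.

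**Inputs.** This trial's response rate R is not in the documents. Assumed values come from the earlier studies in Protocol section 1.1.2.2:

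- Pivotal phase II study: 42.9% locally advanced (27/63) and 30.3% metastatic (10/33).
- Phase I study: 60% locally advanced and 50% metastatic.

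Cohort sizes of 1119 and 96 are the safety counts in the SAP's Summary of Deaths shell. They are upper bounds for the measurable-disease subset. All hazards and median times below are assumptions.

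**Case A: constant competing hazards.** Let h_r be the hazard of response and h_c the hazard of leaving without response, so R = h_r/(h_r + h_c). Then:

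- one minus Kaplan-Meier = 1 − exp(−h_r t), with median t = ln2/h_r;
- true cumulative response at that t = R × (1 − exp(−ln2/R));
- share still at risk at that t = exp(−ln2/R).

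| R | ln2/R | Still at risk | True cumulative response at the Kaplan-Meier median |
|---|---|---|---|
| 30.3% | 2.288 | 10% | 0.303 × 0.898 = 27% |
| 42.9% | 1.616 | 20% | 0.429 × 0.801 = 34% |
| 50% | 1.386 | 25% | 0.5 × 0.75 = 37.5% |
| 60% | 1.155 | 31% | 0.6 × 0.685 = 41% |

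In months, take a total exit hazard h of 0.15 to 0.35 per month. The median among responders is ln2/h = 4.6 down to 2.0 months. The Kaplan-Meier median is ln2/(R × h): 10.8 down to 4.6 months at 42.9%, and 15.3 down to 6.5 months at 30.3%.

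**Case B: fixed responders and non-responders.** Case A makes non-responders leave as fast as responders respond. To relax this, let a share R respond with exponential median m_r, and let the rest be censored with exponential median m_c. Put a = ln2/m_r and b = ln2/m_c. The hazard that Kaplan-Meier accumulates is R·a·exp(−at) / [R·exp(−at) + (1 − R)·exp(−bt)], integrated numerically.

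- R = 30.3%, m_r = 2, m_c = 5.5 or 9.5 months: one minus Kaplan-Meier levels off at 0.43 or 0.37. No median exists, but both values exceed 0.303.
- R = 42.9%, m_r = 2, m_c = 9.5: the median falls at 14.8 months, where true response is 0.429 × (1 − 2^(−14.8/2)) = 42.6%.
- R = 60%, m_r = 2, m_c = 9.5: the median falls at 4.4 months, where true response is 0.6 × (1 − 2^(−4.43/2)) = 47%.

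**Simulation of Case B.** Assessments were on an 8-week grid, with m_r of 2, 3.5 or 5 months and m_c of 3, 6, 9.5 or 15 months (12 scenarios; 100 runs each at N = 1119, 400 at N = 96).

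| | R = 42.9%, N = 1119 | R = 30.3%, N = 96 |
|---|---|---|
| How often a median was reported | 100% of runs in 9 scenarios; 83%, 5% and 0% in the other three | at least 93% of runs in 3 scenarios; 44–56% in 3; 6% or fewer in 6 |
| Mean final value of one minus Kaplan-Meier | 0.47 to 1.00 (true 0.43) | 0.33 to 0.96 (true 0.30) |

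The overstatement is present in every scenario. Whether a median is printed depends on how early non-responders leave assessment relative to response times.

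**The case against.** A reader might infer that the plan will report a median although most patients never respond, and that this will contradict the response-rate table. The documents do not support that. They do not give this trial's response rate, and at the phase I rate of 60% most locally advanced patients do respond. Even at 30.3%, half of the simulated scenarios almost never produced a median.

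Nor can 27% and 34% be taken as the size of the error. They rest on Case A, which fits the pivotal study poorly. There, progression was the best response in only 12.7% (locally advanced) and 3.0% (metastatic) of patients, and median therapy was 9.7 and 10.0 months. For the metastatic cohort, suppose every responder was still on treatment at 10 months. Then 0.303 + 0.697 × 2^(−10/m) = 0.5 gives a non-responder median exit of about m = 5.5 months, and longer if some responders had stopped. That is the setting in which Case B gives no median when responses come quickly.

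Other points reduce the weight:

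- Safety is primary and no hypothesis is tested.
- Response rate is the efficacy variable of primary interest and duration of response the key secondary one.
- The response rate has its own table with a Clopper-Pearson interval, and the time-to-response table carries percentages that may show the share with events. The mock-up is not available to confirm this.
- Patients who stop for reasons other than progression or consent withdrawal stay in follow-up, so stopping treatment is not in itself a competing event.
- Patients still treated past progression may be censored after their progression date.
- The best-response rule does not expressly cover a patient who first met stable disease and then progressed. Treating progression as competing there rests on its ordinarily ending treatment.
- Kaplan-Meier is the protocol's stated method. The SAP is dated 14 September 2015, after the 3 August 2015 snapshot shown in its shells, so deleting the protocol's estimate at that stage would itself need explaining.

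These points limit the certainty, the size and the form of the remedy. They do not repair the estimator: deaths and progressions before response are still handled as though response remained possible.

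**Conclusion.** The concern holds in a limited form. The censoring rule overstates the cumulative probability of response. Any median or quartile from it cannot be read as the time by which that share of patients responded, and a median can appear when fewer than half respond.

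At assumed response rates, true cumulative response at the Kaplan-Meier median is:

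- 30.3%: about 27% under constant hazards, with no median in some mixture scenarios;
- 42.9%: about 34% to 43%;
- 60%: about 41% to 47%.

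The lower figure in each range is Case A. The upper is Case B with a 2-month median response time and a 9.5-month median exit. These are two reference cases, not bounds, and both treat every exit without response as final. Patients still ongoing or lost at the cut are properly censored, so the part of the error due to progression and death alone is smaller by an amount the documents do not allow one to compute. For a secondary, descriptive endpoint this is a cheap improvement, not a threat to the trial's main conclusions.

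**What to change.** Make two summaries the reported results for time to response:

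1. The cumulative incidence of confirmed CR or PR in the same population, with progression or death before response as competing events. Patients still ongoing or lost without progression are censored at their last tumour assessment.
2. The median and range of time to response among confirmed responders.

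If the protocol's Kaplan-Meier estimate is kept, show it only as supplementary, with a footnote that its median is not the time by which half of patients respond.

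The cost is a short SAP paragraph and one program change. Progression and death dates are already needed for PFS, so no new data are required. The downside is a departure from the Kaplan-Meier wording in Protocol section 8.2.1.1, which the report should note.
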